5.1 Patient-level Study Calendar

[Patient-level study calendars for practices randomized to Arms 2 and 3 are provided are Appendices III and X.]

	Screening	Baseline*	Day of Surgery	8 weeks following surgery	12 weeks following surgery
Collected for all eligible (screened) patients					
Postoperative complications and outcomes				X (1)	X (1)
Adverse Event Assessment			X (1)		
Administered to all consenting patients					
Laboratory Studies					
HgB, WBC, Platelets		X		X***	
Serum creatinine		X		X***	
Serum albumin		X		X***	
Tests & Observations**					
ECOG PS		X		X***	
CHAMPS and EQ-5D Qx		X		X***	

* At initial surgical consultation. Questionnaires may be completed at any time following consent, before or after registration. Additionally, sites may leverage satellite NCORP locations to obtain baseline and 8-week follow-up labs and forms.

** Site staff may contact participants via email, U.S. mail, telephone and/or telehealth to administer and obtain questionnaires and assessments, including the CHAMPS Survey and the ECOG Performance Score.

*** Post surgery visits can be +/- 7 days

1. For the purposes of collecting and reporting adverse events into the Alliance database using Rave “adverse events” are those potentially resulting from intervention occurring between baseline and surgery. “Surgical complications” will be assessed 8 and 12 weeks after surgery using the Clavien-Dindo Classification. All CTEP-AERS events should be reported as outlined in [Section 9.0](#).

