7.5.1 Usual Care

These practices will not get the OPTI-Surg intervention. Practices randomized to usual care will complete the practice demographic and structural survey and the ORCA questionnaire at baseline (i.e., as soon as the practice site agree to participate and before training) and at 6, 12, and 24 months following site activation. Two practices randomized to usual care will also undergo staff interviews at baseline, after the fifth patient is enrolled, and 6 to 9 months after the last patient is enrolled to the study at the practice.

For all patients (consented and unconsented) aged ≥ 70 years, practices will keep a log of all patients seen. The practice will submit the log monthly. In addition, the practices will submit data abstracted from patient charts. Practices will report surgical complications for all eligible patients. The log will be a spreadsheet format of the case report form variables.

The CHAMPS and EQ-5D-5L questionnaires will be administered to consenting eligible patients at the time of the initial surgical consultation and 8 weeks after surgery.

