8.5 Surgery and Follow-up (all sites)

Surgery will be performed per the treating physician.

For all patients, **adverse events** occurring from the patient's initial evaluation to surgery will be collected. In addition, **surgical complications** will be assessed 8 and 12 weeks after surgery.

For registered patients only, **the questionnaires (CHAMPS and EQ-5D-5L)** will be administered at 8 weeks.

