9.1 Routine Adverse Event Reporting

Adverse event data collection and reporting, which are required as part of every clinical trial are done to ensure the safety of patients enrolled in the studies as well as those who will enroll in future studies using similar agents. Adverse events are reported in a routine manner at scheduled times according to the study calendar in Section 5.0. For this trial, "Adverse Event: Other" form is to be used for routine AE reporting in Rave.

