9.2 CTCAE Routine Reporting Requirements

In addition to the solicited adverse events listed in Section 9.1, the following table outlines the combinations of time points, grades and attributions of AEs that require routine reporting to the Alliance Statistics and Data Center. Questions about routine reporting should be directed to the Data Manager.

Combinations of CTCAE Grade & Attribution Required for Routine AE Data Submission on Case Report Forms (CRFs)

Attribution	Grade 1	Grade 2	Grade 3	Grade 4	Grade 5
Unrelated			a	a	a
Unlikely			a	a	a
Possible		a	a, b	a, b	a, b
Probable		a	a, b	a, b	a, b
Definite		a	a, b	a, b	a, b

a) Adverse Events: Other CRF - Applies to AEs occurring between registration and within 30 days of the patient's last treatment date, or as part of the Clinical Follow-Up Phase.

- b) Adverse Events: Late CRF - Applies to AEs occurring greater than 30 days after the patient's last treatment date.

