12.5 Study Monitoring

This study will be monitored by the Alliance Data Safety Monitoring Board (DSMB), an NCI-approved functioning body. Reports containing efficacy, adverse event, and administrative information will be provided to the DSMB every six months as per NCI guidelines.

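### Footnote 1 of the patient calendar admits only intervention-related adverse events to Rave; this contradicts 8.5 and 9.2 and, where followed, makes routine pre-surgical counts non-comparable between arms

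*Combined protocol and SAP*

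**What the plan says.** All references are to the combined protocol and SAP.

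- **Section 5.1, footnote 1.** For collection and reporting in Rave, adverse events "are those potentially resulting from intervention occurring between baseline and surgery". The footnote then treats surgical complications separately (Clavien-Dindo, 8 and 12 weeks) and adds that "All CTEP-AERS events should be reported as outlined in" Section 9.0.
- **Section 5.1, calendar body.** The Adverse Event Assessment row, to which the footnote is attached, sits under the line "Collected for all eligible (screened) patients".
- **Section 8.5, headed as applying to all sites.** For all patients, adverse events from the patient's "initial evaluation to surgery will be collected". No attribution condition is stated.
- **Section 9.1.** "Adverse events are reported in a routine manner at scheduled times according to the study calendar in Section 5.0".
- **Section 9.2.** The table gives the "combinations of time points, grades and attributions of AEs that require routine reporting". Grades 3, 4 and 5 are marked as required in the Unrelated and Unlikely rows.
- **Section 7.5.1, on usual care.** "These practices will not get the OPTI-Surg intervention".
- **Section 12.5.** "Reports containing efficacy, adverse event, and administrative information will be provided to the DSMB every six months".

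**The concern.** Attribution is normally a field recorded about an event. Footnote 1 makes it the test for whether the event is recorded at all. In a trial with a usual-care arm that test works differently by arm. A practice without OPTI-Surg has little that could result from it. In a practice with OPTI-Surg, Section 9.0 leaves attribution to the investigator, who knows what the practice was assigned.

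Two errors could follow, in opposite directions. A background rate of events in patients aged 70 or over awaiting major surgery could appear mainly in the OPTI-Surg arms and look like an excess. Or a real excess that staff call unrelated could stay out of the routine record. Sites that follow 9.2 and sites that follow the footnote would also submit different data under one protocol. The period matters because Section 11.1 runs the patient-level intervention until surgery, so these are the weeks in which direct harm from the programme would arise.

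**Working it through.** The plan gives no figure on this point to reproduce. The check is a comparison of the texts and a count of the 9.2 table.

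**1. Attribution**

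| Source | Attribution needed for recording? | Patients |
|---|---|---|
| 5.1, footnote 1 | Yes, potentially from the intervention | Row covers all eligible (screened) patients |
| 8.5 | No | All patients, all sites |
| 9.2 table | No for grades 3-5; Possible or higher for grade 2 | From registration, so registered patients |

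The footnote conflicts with both other sources.

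**2. How much of 9.2 the footnote removes**

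Required cells by row: Unrelated 3 (grades 3-5), Unlikely 3 (grades 3-5), Possible 4, Probable 4, Definite 4 (each grades 2-5).

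Total = 3 + 3 + 4 + 4 + 4 = 18.

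- If neither Unrelated nor Unlikely counts as potentially resulting from the intervention, the footnote removes 3 + 3 = 6 of 18 cells.
- If Unlikely is still counted as potentially resulting, it removes 3 of 18.

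These are the cells that a usual-care practice would mainly use. Two of the six are grade 5, and 9.3 separately requires routine reporting of every death on study, so the cells left without another routine route are the grade 3 and 4 ones: 6 - 2 = 4.

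**3. Collection window**

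- Footnote 1: baseline to surgery.
- 8.5: initial evaluation to surgery. The calendar places baseline at the initial surgical consultation, so these two largely agree.
- 9.2, note (a): registration to 30 days after the last treatment date, or as part of clinical follow-up.

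The 9.2 window differs at both ends, so removing the attribution condition alone would not align the three texts.

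**4. Which text governs**

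No precedence is stated. Two things pull a site towards the footnote: it is the text that defines an adverse event for Rave, and 9.1 sends routine reporting to the calendar. However, 9.1 refers to the calendar for scheduled times and does not say that the footnote overrides the 9.2 attribution table.

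**5. What is captured whatever the attribution**

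- Deaths: routine and expedited reporting (9.3).
- Events equivalent to grade 3-5 that lead to or prolong hospitalization: expedited reporting (9.3).
- Postoperative complications: reported for all eligible patients (7.5.1) and compared between the combined OPTI-Surg arms and usual care, together with other surgical outcomes within 12 weeks (12.4.3).

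The exposed part is therefore the routine Rave record of pre-surgical events. Section 12.4 plans no between-arm analysis of these events, so their main use is the six-monthly DSMB report.

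**The case against.** The best reply is that footnote 1 was meant only to separate pre-surgical events from Clavien-Dindo complications, which its next sentence takes up, and that every other text points to full collection: the calendar row for all eligible patients, 8.5, 9.2, and 13.1.1, which reviews the records of non-consenting patients for adverse events without an attribution condition. The word intervention is also used loosely. Section 4.3.2 counts usual care among the three intervention arms, and 8.0 describes record review at all institutions as part of the patient-level intervention. This may well be the intent. It does not remove the contradiction, because the footnote's wording is definitional and nothing ranks it below 8.5 or 9.2.

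The reply does rule out some stronger readings.

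- *Usual-care practices have nothing to record.* A reader might infer this, but it requires the footnote to override all the texts just listed.
- *Harms cannot be compared between arms.* This is too broad. Complications, mortality and readmission are collected in every arm and compared.
- *Events called unrelated are never recorded.* This is wrong for deaths and hospitalizing grade 3-5 events, and footnote 1 itself sends expedited events to Section 9.0.
- *A probability can be put on a false excess.* With 300 OPTI-Surg and 150 usual-care consented patients, 9/300 against 0/150 gives a two-sided Fisher p of 0.033. But fixing usual care at zero assumes the disputed point. The event rate and the share judged related are not in the documents, and the plan contains no such test. The calculation is at most illustrative, and I do not rely on it.

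One limit also stands. The Arm 2 and Arm 3 calendars are in Appendices III and X, which are not in the text available to me, so I cannot say whether the footnote is repeated there.

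**Conclusion.** The documents contradict themselves on what counts as a recordable pre-surgical adverse event. The footnote drops 6 of the 18 combinations that 9.2 requires (3 if Unlikely is read as potentially related) and adds a condition that 8.5 does not have. Where a site follows the footnote, ascertainment differs by arm, and the routine pre-surgical counts in the DSMB reports cannot be compared with usual care.

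The conclusion is conditional on some sites following the footnote and on the intervention meaning OPTI-Surg. For Arms 2 and 3 it also depends on whether their calendars carry the same wording. How many events would be affected cannot be derived from the documents. The primary and secondary endpoint analyses are not touched. This should be corrected as an inconsistency in safety collection; the documents as a whole do not show a deliberate choice to filter by attribution.

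**What to change.** 1. Delete the attribution condition from footnote 1 of 5.1, and from the calendars in Appendices III and X if it is repeated there.
2. Reconcile footnote 1, 8.5 and 9.2 into one adverse-event definition and one collection window, applied identically in all three arms. Matching attribution alone would leave the 9.2 window mismatch in place.
3. For registered patients, record grade 3-5 pre-surgical events whatever their attribution, as 9.2 already requires, with attribution as a recorded field. Grade 2 events can stay as in the 9.2 table.
4. For non-consenting patients, collect aggregate counts only, since 13.1.1 allows no patient-level record for them.
5. In the DSMB reports, tabulate grade 3-5 pre-surgical events by arm regardless of attribution, with the number of patients assessed as denominator. Any table restricted to related events should be a supplement.

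The cost is a coordinated edit to three sections, possibly two appendices, and one DSMB table. The downside is small: usual-care sites will enter some events that they might otherwise have skipped.

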5.2 Site-level Study Calendar

[Site level study calendars for practices randomized to Arms 2 and 3 are provided in Appendices III and X.]

	Baseline*	Monthly	After 5 th patient is enrolled and 6 to 9 mos. after last patient is enrolled	6, 12 and 24 months
Demographic and structural data	X			
Organizational Readiness to Change Assessment (ORCA)	X			X
Ethnographic interviews and observations	X (1)		X (1)	
Listing of eligible patients		X		
Postoperative Complications			Administered per patient schedule and submitted monthly (3)	

* Following local IRB approval/activation of the study.

1. To be administered to staff at 5 sites randomized to each intervention arm.
3. Clavien Dindo Classification for grading severity of complications and American College of Surgeons' National Quality Improvement Program geriatric outcome variables (Section 10.3.1). To be collected for all eligible patients (including those who do not consent to completing the CHAMPS and EQ-5D questionnaires).

6.0 DATA SUBMISSION

6.1 Data Collection and Submission

Medidata Rave is a clinical data management system being used for data collection for this trial/study. Access to the trial in Rave is controlled through the CTEP-IAM system and role assignments.

Requirements to access Rave via iMedidata:

- A valid CTEP-IAM account; and
- Assigned a Rave role on the LPO or PO roster at the enrolling site of: Rave CRA, Rave Read Only, Rave CRA (LabAdmin), Rave SLA, or Rave Investigator.

Rave role requirements:

- Rave CRA or Rave CRA (Lab Admin) role must have a minimum of an Associate Plus (AP) registration type;
- Rave Investigator role must be registered as an Non-Physician Investigator (NPIVR) or Investigator (IVR); and
- Rave Read Only role must have at a minimum an Associates (A) registration type.

Refer to [REDACTED] for registration types and documentation required.

Upon initial site registration approval for the study in Regulatory Support System (RSS), all persons with Rave roles assigned on the appropriate roster will be sent a study invitation e-mail from iMedidata. To accept the invitation, site staff must log in to the Select Login [REDACTED] using their CTEP-IAM username and password and click on the accept link in the upper right-corner of the iMedidata page. Site staff will not be

able to access the study in Rave until all required Medidata and study specific trainings are completed. Trainings will be in the form of electronic learnings (eLearnings) and can be accessed by clicking on the link in the upper right pane of the iMedidata screen. If an eLearning is required and has not yet been taken, the link to the eLearning will appear under the study name in iMedidata instead of the Rave EDC link; once the successful completion of the eLearning has been recorded, access to the study in Rave will be granted, and a Rave EDC link will display under the study name.

Site staff that have not previously activated their iMedidata/Rave account at the time of initial site registration approval for the study in RSS will receive a separate invitation from iMedidata to activate their account. Account activation instructions are located on the CTSU website in the Data Management section under the Rave resource materials (Medidata Account Activation and Study Invitation Acceptance). Additional information on iMedidata/Rave is available on the CTSU members' website in the Data Management > Rave section at [REDACTED] or by contacting the CTSU Help Desk at [REDACTED]

A Schedule of Forms is available on the Alliance study webpage, within the Case Report Forms section. The Schedule of Forms is also available on the CTSU site within the study-specific Education and Promotion folder, and is named Time & Events.

Patient-completed questionnaire booklets for this study are to be ordered prior to the registration of any patients (see Section 4.4). Samples of questionnaire booklets are available in Appendix I for reference and IRB submission only. They are not to be used for patient completion. Booklets must be given to patients to complete and patients should be instructed to return the booklets to site staff either in person or by mail and site staff will enter patient and caregiver responses into Rave.

6.1.1 Data Quality Portal

The Data Quality Portal (DQP) provides a central location for site staff to manage unanswered queries and form delinquencies, monitor data quality and timeliness, generate reports, and review metrics.

The DQP is located on the CTSU members' website under Data Management. The Rave Home section displays a table providing summary counts of Total Delinquencies and Total Queries. DQP Queries, DQP Delinquent Forms and the DQP Reports modules are available to access details and reports of unanswered queries, delinquent forms, and timeliness reports. Review the DQP modules on a regular basis to manage specified queries and delinquent forms.

The DQP is accessible by site staff that are rostered to a site and have access to the CTSU website. Staff that have Rave study access can access the Rave study data using a direct link on the DQP.

To learn more about DQP use and access, click on the Help icon displayed on the Rave Home, DQP Queries, and DQP Delinquent Forms modules.

Note: Some Rave protocols may not have delinquent form details or reports specified on the DQP. A protocol must have the Calendar functionality implemented in Rave by the Lead Protocol Organization for delinquent form details and reports to be available on the DQP. Site staff should contact the LPO Data Manager for their protocol regarding questions about Rave Calendaring functionality.

6.1.2 Supporting Documentation to be Submitted to the Alliance

This study requires supporting documentation for diagnosis and treatment of the cancer that is the target of the planned surgery. Supporting documentation will include:

- Preoperative imaging reports (CT, MRI, PET/CT).
- Operative reports.
- Surgical pathology reports.

Supporting documentation is to be submitted via Rave. Note: The pre-operative imaging is to be submitted within 12 weeks after registration.

6.1.3 Practice level data

Demographic and Structural Data: At baseline, the study team will collect basic practice-related demographic information and details regarding the organizational structure and resource availability (e.g., practice volume; payer mix; solo, single specialty, or multi-specialty group practice; availability of geriatric specialists, palliative care providers, advanced practice providers, patient navigators, on site occupational and physical therapy, social workers, pharmacists, dietetics, integrative medicine).

Qualitative Data: The team will collect qualitative data to document practice-level barriers and facilitators to OPTI-Surg implementation from 12 practices: 5 each from the two OPTI-Surg arms and 2 practices from the usual care arm. In-person site visits to collect qualitative data will take place at the following time points: Baseline (prior to the introduction of the OPTI-Surg intervention); after the fifth patient has been enrolled at the practice; and 6 to 9 months after the last patient has been enrolled at the practice. Qualitative data will be collected via direct observation of clinic processes and key-informant interviews with practice leadership and with front-line staff.

7.0 STUDY IMPLEMENTATION

7.1 Eligible Practices

Eligible practices will be engaged in elective cancer operations that are high risk in older adults. Based on administrative data on operative mortality, the following have been identified as high risk in older adults: gastrectomy 3-10%; colectomy 1-2%; proctectomy 2%; esophagectomy 6-16%; pancreatectomy 2-10%; hepatectomy 3-7%; nephrectomy 2%; total cystectomy 3%; and lung lobectomy/pneumonectomy 3-9%.

Eligible practices will have a high prevalence (at least 10 cases per year) of patients among whom there is a high risk of frailty (age ≥ 70 years old) and be categorized as either a thoracic, major abdominal, or urologic practice. Practices should identify a clinical research professional, allied health professional, or equivalent to implement OPTI-Surg.

Eligible practices should provide a brief description of any existing programs for frailty assessment and intervention. If their current practice includes the assessment and interventions specified in the protocol, they will be ineligible.

See Section 4.3.1 for information regarding site approval procedures.

7.2 OPTI-Surg Toolkit

For practices randomized to Arm 2, see Appendix III; For practices randomized to Arm 3, see Appendix X.

7.3 Institutional training

[figure not shown]
For practices randomized to Arm 2, see Appendix III; For practices randomized to Arm 3, see Appendix X.

7.4 Randomization

Randomization will be stratified by practice type (thoracic, major abdominal, and urologic). Pocock-Simon dynamic allocation with a 5% level of randomness (to ensure that the algorithm is not deterministic) added to the algorithm such that practices will be assigned to the arm in a 1:1:1 fashion that leads to more imbalance 5% of the time. Site randomization will be centrally performed by the Alliance Statistical and Data Center once an institution is interested and eligible to participate (see Section 4.3).

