4.3 Institutional randomization and arm-specific protocols

4.3.1 Institutional Registration

Institutions that are interested in participating in this study must contact the study Project Manager, [REDACTED] for site approval procedures:

Sites should complete the information required in the Institutional Approval Document posted along with Supplementary materials on the Alliance and CTSU websites, and send it to [REDACTED] at the email address listed above. The document will ask for the following information: Name of the site, CTEP Site Code, CTEP Site Code of Main NCORP and contact information (Full name and email) of site staff who will complete the site/practice survey in Medidata Rave.

To approve the site for participation, the project manager will return this document to the institution with a signature of approval. As soon as the site receives IRB approval, it must submit this Institutional Approval Document to the Alliance Registration Office via fax [REDACTED] or email at [REDACTED]. The registration office will register the site to the study and send confirmation to the site via email within 1 business day, in order to be invited to enter site level data in Medidata Rave. The study will not use OPEN for site/practice enrollment. The contact person listed on the Institutional Approval Document will be sent an invitation to enter site level data in Medidata Rave.

Additionally, the site will also submit this document to the CTSU Regulatory portal (see Section 4.2.3) in order to begin patient enrollment.

4.3.2 Randomization will be stratified by practice type (thoracic, major abdominal, and urologic).

The Alliance Statistics and Data Management Center will randomize surgical practices once an institution is interested and eligible to participate. All participants enrolled at a site will receive the intervention to which the treating institution is randomized.

Institutions will be randomized to one of three intervention arms:

- 1) Usual Care
- 2) OPTI-Surg without coach
- 3) OPTI-Surg with coach

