4.3.3 Intervention-specific appendices

In order to maintain institutional blinding with respect to OPTI-Surg interventions, information specific to the OPTI Surg arms is provided separately in Appendices III and X. Following randomization, practices should contact [REDACTED] [REDACTED] [REDACTED] to obtain the appendices specific to the intervention arm to which the practice has been randomized. The OPTI-Surg Toolkit/Manual will also be provided to sites at this time.

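### The stated trigger lets a practice be randomised, and learn its arm, before IRB approval, site registration or its baseline survey

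*Combined protocol and SAP*

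**What the plan says.** Two sections state when a practice is randomised. Section 7.4: "Site randomization will be centrally performed by the Alliance Statistical and Data Center once an institution is interested and eligible to participate". Section 4.3.2: "The Alliance Statistics and Data Management Center will randomize surgical practices once an institution is interested and eligible to participate". Both rest on interest and eligibility alone.

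Section 4.3.1 describes the site's path. It opens with interest: "Institutions that are interested in participating in this study must contact the study Project Manager". Project-manager approval, IRB approval, registration and the invitation to enter site-level data follow. On IRB approval it says: "As soon as the site receives IRB approval, it must submit this Institutional Approval Document to the Alliance Registration Office". Randomisation is not placed in that sequence. Section 7.1 defines an eligible practice by case volume, practice type, a named person to implement the toolkit and the absence of an equivalent programme. It refers to 4.3.1 separately for site approval.

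Arm disclosure follows allocation. Under Section 4.3.3, "Following randomization, practices should contact" the study office "to obtain the appendices specific to the intervention arm to which the practice has been randomized".

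The baseline structural survey and ORCA are timed in two ways. The footnote to the site calendar in Section 5.2 reads "Following local IRB approval/activation of the study". Section 7.5.1 reads "as soon as the practice site agree to participate and before training", and Section 10.3.3 similarly links ORCA to the site's agreement. None of these mentions randomisation.

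**The concern.** In a cluster trial the allocated unit should be committed, and its baseline recorded, before anyone there knows the arm. Otherwise a practice disappointed by usual care, or daunted by the toolkit, can decline to open. The loss then depends on the arm and removes a whole cluster.

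The analysis would not show it. The primary model (Section 12.4.2) uses consented patients with baseline and 8-week CHAMPS. The complication and screening analyses (Section 12.4.3) use eligible patients from practice records. A practice that never opened supplies neither. With 10 practices per arm, one loss is a tenth of the arm.

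ORCA asks staff to rate the evidence for OPTI-Surg and to say how leadership would act if it were introduced (Appendix II). Answers given with the arm known may reflect the allocation as well as prior readiness.

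**Working it through.** **Order of steps.** Section 4.3.1 gives: interest, project-manager approval, IRB approval, registration, invitation to enter site data. Interest is the first step, and eligibility as defined in 7.1 contains none of the later ones. Read literally, the trigger can be met before IRB approval. Under the Section 5.2 footnote the baseline survey would then follow allocation. Under Section 7.5.1 it could come before or after. The text permits either order and requires neither.

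**Inputs for power** (Section 12.3): 59% frail; screening 60% and 80%, average 70%; SD 18.3 kcal; intracluster correlation 0.005; 11 evaluable patients at each of 30 practices, so 110 usual care and 220 combined OPTI-Surg; two-sided alpha 0.05.

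**The plan's own figures.**
- Usual-care mean: 0.59×8 + 0.41×18 = 12.10.
- OPTI-Surg mean: 0.59×(0.7×23 + 0.3×8) + 0.41×(0.7×23 + 0.3×18) = 0.59×18.5 + 0.41×21.5 = 19.73.
- Difference 7.63; 7.63/18.3 = 0.417 SD (stated 0.42).
- Variance inflation factor (VIF): 1 + 10×0.005 = 1.05, as stated.
- Fixed-design power: SE = √(1.05/110 + 1.05/220) = 0.1197; 0.417/0.1197 = 3.48; Φ(3.48 − 1.96) = 93.6%.
- If the futility rule in Section 12.1 (p ≥ 0.323, read as two-sided, at half the information) is always acted on, power is 89.5%, or 89.9% at exactly 0.42. This agrees with the stated 90%.

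**Illustrative loss of usual-care practices, 20 OPTI-Surg practices kept.** The number lost is an assumption.

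Not made up: SE = √(1.05/n + 1.05/220), with n = 11 × practices left.

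Made up by the remaining sites: usual care stays at 110 evaluable, with larger clusters.
- 8 sites: 110/8 = 13.75 each, VIF 1 + 12.75×0.005 = 1.064.
- 7 sites: 110/7 = 15.71 each, VIF 1 + 14.71×0.005 = 1.074.
- Consented patients needed per site: 150/8 = 18.75 or 150/7 = 21.4, both under the cap of 25.

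| Practices lost | Fixed design, not made up | Fixed design, made up | Futility rule always followed, not made up |
|---|---|---|---|
| 0 | 93.6% | – | 89.5% |
| 2 | 89.7% | 93.4% | 84.7% |
| 3 | 86.7% | 93.3% | 81.2% |

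**Illustrative bias.** If 2 of 10 usual-care practices leave and their mean differs from the other eight by an assumed 2 to 6 kcal, the usual-care mean shifts by 0.2×2 = 0.4 to 0.2×6 = 1.2 kcal. That is 0.4/7.63 = 5% to 1.2/7.63 = 16% of the planned effect. Recruiting more patients at the same eight sites leaves this shift unchanged.

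**The case against.** The strongest reply is that the documents never say randomisation comes before IRB approval. Section 4.3.2 is printed after the registration steps of 4.3.1, Section 7.4 refers back to 4.3, and Section 7.1 ends by pointing to 4.3.1, so being eligible to participate might be taken to include completing those steps. The institutional randomisation schema and Appendices III and X are also not in the text examined, and may show the order. This stands against a reader who infers that practices are in fact randomised before approval. It does not supply the missing requirement: neither section that governs randomisation makes approval, registration or a completed survey a condition.

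On the survey, Sections 7.5.1 and 10.3.3 tie ORCA to agreement, which may be as early as the randomisation trigger. So it cannot be said that baseline ORCA is completed after allocation, only that it may be. A reader might also infer that this damages objective 2.3.2. That objective concerns structural factors such as volume and payer mix, which knowledge of the arm would hardly alter. ORCA serves the exploratory work on barriers and facilitators, and no primary or secondary analysis uses it.

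On power, Section 12.1 lets the number of practices change when per-practice enrolment is slow, and Section 12.3 lets a site enrol up to 25 patients. The larger losses in the table need both no make-up and a non-binding futility rule that is always followed. That criticism is right.

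Finally, withholding arm-specific materials until randomisation limits what practices know beforehand. It does not stop withdrawal once the arm is known.

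**Conclusion.** The point holds as a gap in the stated rule: the protocol permits allocation and arm disclosure before a practice has approval, registration or baseline data. It does not show that this order was intended or that any practice was lost.

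The main risk is bias from losing different kinds of practice in different arms, which extra patients or practices cannot repair. Its size is unknown; the 5% to 16% above rests on an assumed two losses and an assumed difference of 2 to 6 kcal. The effect on power is modest: with two usual-care practices lost, about 90% (fixed design) if their patients are not made up and about 93% if they are, against 93.6% with none lost. A reader might infer from the 84.7% figure that the trial would be seriously underpowered. The documents do not support that, since they give no withdrawal rate and allow the patients to be made up.

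**What to change.** In Sections 4.3.2 and 7.4, state that a practice is randomised only after IRB approval, site registration, and receipt of its baseline ORCA and structural survey. Align the survey timing in Sections 5.2 and 7.5.1 with that order. In the analysis report, give the numbers of practices randomised, activated and enrolling by arm, including those with no patients. For practices already randomised, also report survey dates relative to allocation.

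The cost is a change of wording and a slightly later start to training in Arms 2 and 3. The change does not remove the whole risk, because a practice can still fail to enrol after activation; the counts by arm would at least make that visible.
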